4.5.2 Medical History

General medical history will be coded using the Medical Dictionary for Regulatory Activities (MedDRA) version 18.1. A summary of medical history by system organ class (SOC) and preferred term (PT) will be presented as frequencies and percentages for each treatment group and overall.

Medical history will also be listed. The listing will be sorted by treatment group, subject identification number, SOC, PT, and reported term.

4.5.3 Concomitant Medications

Study medications will be coded using the World Health Organization (WHO) Drug dictionary version Sep2015 (WHODDE+HERBAL). Medications and all information collected will be reported as collected via the eCRF.

Prior medications are medications defined as those that stop before the first dose.

Concomitant medications (CMs) are medications taken during the study, including any medication that was ongoing at the time of first dose, medication taken on or after the first dose of study drug, or any medication started prior to the last treatment dose.

Partial date rules for flagging concomitant medications will follow the rules detailed in the AEs. In case of missing dates, a medication will be considered as concomitant.

A summary of CMs will be presented as frequencies and percentages for each treatment group and overall.

Prior and CMs will also be listed.

4.6 Treatment Compliance

4.6.1 SUVN-502 Compliance

Study medication compliance will be assessed during the Treatment Period.

Treatment Compliance is calculated as:

$$\frac{\text{Number of compliant days}}{\text{Expected number of compliant days}} \times 100\%$$

Number of compliant days is the number of days on which double-blind treatment was taken. Number of compliant days is calculated by the number of tablets dispensed less number of tablets returned at the next visit.

Expected number of compliant days is the number of days double-blind treatment is scheduled based on the subject's duration of participation in the study, excluding the follow-up phase.

In cases where the bottle is not returned at Week 4/Week 13/Week 30 and non-compliance was not reported by the subject or caregiver, the number of compliant days will be calculated based on the number of pills dispensed and capped at the number of pills they should have taken during the specific time period. That is, if there were 35 tablets dispensed at Baseline, and the subject does not return the bottle at Week 4, the number of compliant days will be 28 (if Week 4 occurs on Day 28). If non-compliance is reported when there are bottles not returned, the compliance for that subject will not be included in the summaries.

[REDACTED]

[REDACTED]

[REDACTED]

- [REDACTED]
- [REDACTED]
- [REDACTED]

The number of subjects considered compliant will be summarized for each timepoint by treatment group.

A listing of treatment compliance will be provided.

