5.3 Packaging, Labeling and Storage

5.3.1 Investigational Treatment: SUVN-502 and Matching Placebo

SUVN-502 will be supplied as identically appearing tablets that contain either 50 mg or 100 mg of SUVN-502. Placebo tablets matching SUVN-502 tablets will also be supplied. SUVN-502 50 mg, SUVN-502 100 mg and matching placebo will be provided in bottles containing 35 tablets. The study drugs will be packaged by the Sponsor according to all local legal requirements. Study drug will be labeled in accordance with applicable regulatory requirements.

All supplies must be stored in accordance with the manufacturer's instructions or in accordance with USP Controlled Room Temperature (20–25°C [68–77°F] with excursions permitted between 15 and 30°C [59 – 86°F]). Until dispensed to the subjects, the study drug will be stored in a securely locked area, accessible to authorized personnel only.

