5.6 Compliance

Note that the caregiver is responsible for holding, dispensing, and returning study drugs and for overseeing all medications.

As part of the routine recording of the amount of study medication (including SUVN-502 or placebo tablets, donepezil HCl, and memantine HCl if provided by the Sponsor) taken by each subject, the caregiver will return study medication at each clinic visit, including

empty bottles (beginning at Visit 3) and the number of tablets remaining in the study packaging will be counted and recorded. These results will be used to calculate subject compliance. Instances where the subject took more or less study medication than prescribed will be recorded on the eCRF.

To monitor for potential for misuse, the site will document significant discrepancies in drug returns where the caregiver returns less study medication than expected but denies taking extra study medication (e.g., lost or missing medication equivalent to more than one tablet per week).

In addition to routine surveillance of subject study medication compliance, subjects/caregivers will be given study drugs “calendar sleeves” which affix to the exterior of study medication bottles to help subjects remember when to take study medication. These sleeves will also help subject/caregiver to remember when the subject missed a dose. These sleeves will be provided to the site and the site will slide them onto the bottles. The site will then instruct the caregiver on how to make them subject-specific (i.e., document on the “calendar sleeve” the date to start taking study medication, bottle number).

When the subject/caregiver returns to the clinical site, the site will perform a tablet count and also review the “calendar sleeve” to verify tablet count and any possible missed or extra doses taken. If there is a discrepancy between the bottle and the “calendar sleeve” subject/caregiver verbal account will be the final decision for which to document in the eCRF. Discrepancies should be documented in the site’s source documents and the reasoning for what was ultimately recorded in the eCRF.

For subjects who discontinue study medication early but remain in the study, site personnel should ensure the subject returns all study medication at the early termination visit. Subjects and caregivers will also be reminded to continue background therapy for Alzheimer’s disease (donepezil HCl and memantine HCl).

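### SAP 4.6.1 treats unreturned bottles asymmetrically: silent non-return is credited up to the tablets due, while subjects who report non-compliance are left out of the compliance summaries

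*SAP*

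**What the plan says.** SAP 4.6.1 defines compliance as compliant days divided by expected days. Compliant days are "calculated by the number of tablets dispensed less number of tablets returned at the next visit", and expected days come from the subject's "duration of participation in the study, excluding the follow-up phase".

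Two rules cover a bottle that is missing:

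- **Nothing reported.** "In cases where the bottle is not returned at Week 4/Week 13/Week 30 and non-compliance was not reported" by subject or caregiver, "the number of compliant days will be calculated based on the number of pills dispensed and capped" at the number due for that period. In the SAP's example, 35 tablets go out at Baseline, the bottle is not back at Week 4 (Day 28), and 28 compliant days are credited.
- **Non-compliance reported.** "If non-compliance is reported when there are bottles not returned, the compliance for that subject will not be included in the summaries".

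The lines directly after these rules are redacted. SAP 4.6.2 uses the same calculation for donepezil and memantine. For Namenda XR and Namzaric, which subjects supply themselves, it uses the capsule count recorded on the eCRF.

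Protocol 8.4 gives the same ratio but no rule for unreturned bottles. Protocol 5.6 does collect intake independently of the SAP rule: "Instances where the subject took more or less study medication than prescribed will be recorded on the eCRF". It also provides calendar sleeves and lets the verbal account decide when sleeve and bottle disagree.

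**The concern.** The same gap in the evidence, a bottle that did not come back, leads to opposite treatment depending on whether anyone spoke up. Silence normally earns 100% for the interval without a count. A report of non-compliance removes the subject. The exclusion sentence carries no visit limit, so read literally one missing bottle can take out a subject's whole compliance figure, including intervals with good tablet counts.

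The subjects removed are those for whom the trial has positive information that dosing was not as prescribed, and Protocol 5.6 already has that information entered on the eCRF. What is at stake is a descriptive table. Readers use it to judge whether a null or a positive result reflects drug actually taken.

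**Working it through.** **1. The SAP's own example.** Credited days = min(tablets dispensed, tablets due) = min(35, 28) = 28. Compliance = 28/28 = 100%. This reproduces the SAP figure.

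**2. The next listed interval.** From Week 4 (Day 28) to Week 13 (Day 91), 63 tablets are due. Protocol 5.3.1 says that active drug and "matching placebo will be provided in bottles containing 35 tablets". If whole bottles are dispensed to cover the interval, two are needed, or 70 tablets, and min(70, 63)/63 = 100%. So the credit is full in both double-blind intervals that close at a listed visit. Together these are 91 of 182 days.

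**3. Direction of the exclusion rule.** Let r be the share of subjects excluded as reporters, q their true mean compliance and m the mean of everyone else. The mean with reporters is (1 − r)m + rq; without them it is m. The shift is r(m − q).

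- It is positive if q < m (under-use) and negative if q > m (over-use).
- With assumed m = 95% and q = 60%: r = 1% gives 0.01 × 35 = 0.35 points; r = 5% gives 0.05 × 35 = 1.75 points.

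**4. Both rules together (illustration only).** The documents give none of n, t, s or the 95%; all are assumptions. Let n = share of subjects with a non-return, t = percentage they actually took throughout, s = share of them who are silent, D = days credited in full out of 182, and 95% for everyone else.

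- Credited value for a silent subject: c = (100D + t(182 − D))/182
- True mean = 95(1 − n) + nt
- Mean under the rules = (95(1 − n) + nsc)/((1 − n) + ns)

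| n | t | D | s | c | True | Under the rules | Difference |
|---|---|---|---|---|---|---|---|
| 10% | 50 | 28 | 1 | 57.69 | 90.5 | 91.27 | +0.77 |
| 10% | 50 | 28 | 0.5 | 57.69 | 90.5 | 93.04 | +2.54 |
| 10% | 50 | 91 | 1 | 75 | 90.5 | 93.00 | +2.50 |
| 10% | 50 | 91 | 0.5 | 75 | 90.5 | 93.95 | +3.45 |
| 2% | 90 | 28 | 1 | 91.54 | 94.9 | 94.93 | +0.03 |
| 2% | 90 | 28 | 0.5 | 91.54 | 94.9 | 94.97 | +0.07 |
| 2% | 90 | 91 | 1 or 0.5 | 95 | 94.9 | 95.00 | +0.10 |

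If t = 100 and s = 1, then c = 100 and the difference is zero.

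**5. Effect of keeping reporters.** Take n = 10%, t = 50, D = 91, s = 0.5. Retaining the reporters at their recorded 50% gives 85.5 + 0.05 × 75 + 0.05 × 50 = 91.75. The gap to the true 90.5 falls from 3.45 to 1.25 points. What remains comes from the credit to silent non-returners, which a sensitivity summary would expose.

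**6. The visit list.** The credit rule names Weeks 4, 13 and 30. What comes back at Week 30 is washout placebo (Protocol 5.1.1), although 4.6.1 excludes follow-up. Week 26, when drug dispensed at Week 13 is checked (Protocol 7.2.5), is not named. The two do not fit together in the visible text.

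**The case against.** The strongest reply is that the bias is assumed rather than shown. Protocol 5.6 records over-use as well as under-use, and leaving out an over-user does not raise the mean. If silent non-returners took every tablet, the credit adds no error. The cap also lowers the figure that dispensed-less-returned would give if nothing came back (35/28 = 125% becomes 100%). The illustration puts non-returners below everyone else, so it can only come out positive. All of this stands, and it is why the direction is conditional and the sizes are only illustrations.

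The plan also discloses a good deal. There is a compliance listing (SAP 4.6.1), the number of non-missing observations is reported (4.2.5), and non-compliance is by default a major deviation summarised by arm (4.3.2). These let a reader see that subjects are missing. They do not correct the summary itself.

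Treating reporters without bottles as missing could be defended if nothing else were known about them. Here intake is meant to be recorded, and SAP 4.6.2 already relies on eCRF counts for Namenda XR and Namzaric.

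Four stronger readings are tempting but not supported:

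- A reader might infer that someone returning nothing at Week 26 scores 105/91 = 115%. That takes an unknown return as zero returned, and the redacted lines may deal with Week 26.
- A reader might extend full credit to all 182 days and obtain 4.8 to 5.0 points on the 26-week mean. The printed rule does not name Week 26.
- A reader might cite Protocol 5.6, where "the site will document significant discrepancies in drug returns where the caregiver returns less study medication than expected", as proof that a short return means missed doses. That sentence is about monitoring for misuse.
- A reader might infer that using Week 26 plasma levels for EP inclusion (SAP 4.6.2) favours one arm or threatens the blind. The criteria and the SAP's EP definition are redacted, so neither can be judged.

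**Conclusion.** The asymmetry is on the face of SAP 4.6.1, and it selectively removes known non-compliers from a reported table. It raises the compliance figures to the extent that reports are mainly of under-use and silent non-returners took less than they were credited with. The size cannot be derived from the documents. Under the stated assumptions it runs from 0.03 to 3.45 points on the 26-week mean; it can be zero, and it could reverse if reports were mainly of over-use. The sponsor-supplied donepezil and memantine tables inherit the method. The primary mITT analysis is untouched, and no effect on the EP is shown. This is a minor point, worth acting on because the correction is cheap and uses data the trial already plans to collect. The visit-list mismatch is a wording query, subject to the redacted text.

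**What to change.** In SAP 4.6.1:

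1. Keep subjects who report non-compliance in the summaries. Calculate their compliant days from the missed or extra doses recorded on the eCRF, and set to missing only those intervals for which no amount was recorded.
2. Report the number of subjects with unreturned bottles by arm and visit.
3. Beside the full-credit version, show one sensitivity summary in which intervals with silent non-return are treated as undetermined.
4. Unless redacted text already does so, reconcile the Week 4, 13 and 30 list with the exclusion of follow-up and with the Week 26 compliance check, and say whether the cap applies to the Week 13 to Week 26 interval.

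Apply items 1 to 3 to donepezil and memantine in 4.6.2.

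The cost is some SAP wording, a count of unreturned bottles and one extra table. Reported compliance is likely to be slightly lower.

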4.6.2 Concomitant Medication Compliance

Compliance will be summarized for each concomitant medication separately- donepezil HCl, memantine HCl, Namenda XR[®], and Namzaric[™].

Compliance for donepezil HCl and memantine HCl will be calculated in the same manner as the SUVN-502 study drug. Namenda XR[®] and Namzaric[™] are provided by the subject on those medications, so the number of capsules taken will be recorded in the eCRF and used in the calculation.

Treatment compliance will be summarized for each concomitant medication by treatment groups between each visit using descriptive statistics, where the expected number of compliant days is the number of days between visits.

[REDACTED]

- [REDACTED]
- [REDACTED]
- [REDACTED]

The number of subjects considered compliant will be summarized for each timepoint by treatment group.

A listing of treatment compliance for each treatment will be provided.

[REDACTED]

[REDACTED]

- [REDACTED]
- [REDACTED]
- [REDACTED]

The compliance calculations for M1 of SUVN-502 subjects in the placebo group will not be calculated.

Week 26 plasma PK concentration data will also be used to determine inclusion into the EP in cases where accountability cannot be determined.

4.7 Efficacy Evaluation

4.7.1 Hypotheses

The primary and secondary analyses will compare each dose of SUVN-502 with placebo. The null hypothesis for each dose of SUVN-502 will be that there is no difference between SUVN-502 and placebo. The alternative hypothesis will be that there is a difference. Symbolically, this is expressed as follows:

$$H_0: \hat{\mu}_{SUVN-502\ 50\ mg} = \hat{\mu}_{placebo}$$

$$H_a: \hat{\mu}_{SUVN-502\ 50\ mg} \neq \hat{\mu}_{placebo}$$

and

$$H_0: \hat{\mu}_{SUVN-502\ 100\ mg} = \hat{\mu}_{Placebo}$$

$$H_a: \hat{\mu}_{SUVN-502\ 100\ mg} \neq \hat{\mu}_{Placebo}$$

where $\hat{\mu}$ is the mean change from baseline.

4.7.1.1 Statistical Methods

Efficacy data will be analyzed using a mixed effects model for repeated measures (MMRM). The model will include fixed categorical factors for treatment, week, treatment-by-week interaction, and APO-E status (carrier- one allele, carrier- two alleles, and non-carrier), as well as a continuous covariate of baseline score, the baseline score-by-week interaction, age, and Baseline MMSE score. Pooled site, as defined in [Section 4.2.4](#), will be included as a random effect. An unstructured covariance matrix will initially be used to model the variation within subjects for the repeated measures. The Least Square (LS) means of each treatment group, and the differences between each SUVN-502 dose group (50 mg and 100 mg) and placebo will be reported for Weeks 4, 13, and 26, along with the corresponding 95% confidence intervals and p-values. See [Section 4.7.2](#) for further details.

4.7.1.2 Handling of Dropouts or Missing Data

For the primary efficacy analyses missing total scores will be maintained as missing. Under the MMRM model, missing data is assumed to be missing at random. However, sensitivity analyses to assess the impact of missing data will also be conducted. These analyses will utilize the same method as described for the primary and secondary endpoints, however, missing total scores will be imputed using the z-score Last Observation Carried Forward (zLOCF) approach prior to analysis. That is, the missing value will be imputed as the score that is the same number of standard deviations from the treatment group mean at that time point as at the subject's last observed value. The missing values will be imputed using this method. Then the imputed values will be recalculated using the newly imputed data in the calculation of the treatment group means. The value that is the same number of standard deviations from that treatment group mean will be used in the analysis. It is noted that the zLOCF approach is unbiased when dropouts are missing at random within the treatment groups or missing at random after taking into account the severity at the time of dropout.

If the proportion and/or pattern of missing data is found to be different to that expected, additional sensitivity analyses may be required. These will be documented in the CSR.

Handling of Missing Items in Calculating Totals

All total and subscale scores for efficacy will be derived from individual items. If any of the individual items are missing or unknown, every effort will be made to obtain the score for the missing item or items. If individual items that derive the total score are missing and fit the below criteria, then the remaining non-missing items will be used to impute the total score. This imputation is independent of the sensitivity analysis described at the beginning of this section and will be used for the primary and secondary analyses.

For the ADAScog-11, if less than 30% (fewer than 21 points) of the total score is missing, the total score (maximum 70) will be imputed using the available non-missing data. If the missing item is available at previous visits, then the missing data will first be imputed using straight line imputation. That is, a simple regression line will be fitted to interpolate or extrapolate the missing item. If the extrapolated value is outside of the range of the item, then the value will be cut off at the maximum/minimum value and will be used in the calculation of the total score. If there are items that have no non-missing values for that subject, then the total remaining items will be multiplied by a factor that includes the maximum score for the missing items. For example, if the first item, "Word Recall Task," which ranges from a score of 0 to 10 (maximum=10) is missing, and the second item "Commands," which ranges from a score of 0 to 5 (maximum=5) is missing, then the multiplication factor= $70/(70-[10+5])=70/55=1.27$. Thus, the total score for this example is the sum of the remaining 9 items multiplied by 1.27. The imputed number will be rounded up to the nearest integer. Specifically, if the sum of the items not including the missing "Word Recall Task" and "Commands," is 50, then the imputed score is $50*1.27=63.5$. So, the imputed total score for this subject, would be 64. If more than 30% of the total score is missing, the total score for the ADAScog-11 at that visit will be considered missing.

The same approach will be used for missing items in the ADCS-ADL and CDR-SB. The only exception is that the imputed total score for CDR-SB will not be rounded up to the nearest integer.

For all other scales, if any item is missing, any total or sum involving that item will be considered missing. This includes MMSE, NPI, and C-SDD.

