Safety analyses will be performed on the Safety Population (SP), defined as all randomized subjects who receive at least one dose of study medication. Pharmacokinetic (PK) analyses will be performed on the SP.

Statistical analysis of the primary endpoint will be performed using mixed model repeated measures (MMRM) without imputation of missing data. The MMRM model will include fixed categorical effects for treatment, pooled site, week, and treatment-by-week interaction, as well as a continuous covariate of baseline score and baseline score-by-week interaction. An unstructured covariance matrix will be used to model the variation of the repeated measures within patient.

The primary efficacy analysis will compare the effect of each dose of SUVN-502 (50 mg and 100 mg), separately, to the effect of placebo, for the change from baseline to week 26 of the ADAS-Cog score using the modified ITT population and the above mentioned MMRM model. No adjustment for multiplicity will be made.

Secondary efficacy analyses include the comparison of the effect of SUVN-502 (50 mg and 100 mg) to the effect of placebo using the same MMRM approach as described above for the following measures:

- ADAS-Cog at Weeks 4 and 13
- CDR-SB at Weeks 4, 13 and 26
- MMSE at Weeks 4, 13 and 26
- ADCS-ADL at Weeks 4, 13 and 26
- NPI at Weeks 4, 13 and 26
- C-SDD at Weeks, 4, 13 and 26

Sensitivity analyses for the primary and secondary variables using last observation carried forward (LOCF) and using the EP analysis set will be conducted.

Exploratory analyses of the primary and secondary efficacy criteria will be conducted based on APO-E4 carrier status.

Schedule of Procedures

Study period	Screening	Baseline	Treatment Period		End of Treatment	Follow-up
Time	Days -28 to -14 ^a	Day 1 ^a	Week 4 Day 28±2	Week 13 Day 91±2	Week 26 Day 182±3 or early withdrawal	Week 30 Day 210±2
Visit number	1	2	3	4	5	6
Procedures						
Informed Consent	X					
Inclusion / Exclusion Criteria	X	X				
Demographics, Medical History	X	X				
Prior and Concomitant Medications	X	X	X	X	X	X
MRI or CT Scan (if Necessary)	X					
Blood Sample for APO-E Genotype Testing		X				
Study Treatment Dispensation ^b		X	X	X	X	
MMSE and ADAS-Cog	X	X	X	X	X	
Modified Hachinski Ischemic Scale	X					
CDR-SB, ADCS-ADL, and NPI		X	X	X	X	
C-SDD	X	X	X	X	X	X
C-SSRS	X	X	X	X	X	X
Review of AEs	X	X	X	X	X	X
Laboratory Tests	X ^c	X	X ^d	X	X ^c	X
Blood Pressure Measurements	X	X	X	X	X	X
ECG	X	X	X ^e	X ^e	X ^e	X

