7.2.7 Early Termination and Follow-Up Visits

Subjects who discontinue early from the study should, if possible, have an Early Termination visit. This visit should take place as soon as possible after the subject stops taking study drug. The observations and procedures scheduled for Visit 5 (Week 26) should be performed at the Early Termination visit. If the subject agrees, he/she should return for a follow-up visit 4 weeks later. The observations and procedures scheduled for Visit 6 should be performed at the Follow-up visit.

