8.5.1.2 Statistical Methods

Change from baseline in ADAS-Cog score will be analyzed using a mixed effects model for repeated measures (MMRM) based on mITT population. The model will include fixed categorical factors for treatment, pooled site, week, and treatment-by-week interaction, as well as a continuous covariate of baseline score and the baseline score-by-week interaction. An unstructured covariance matrix will be used to model the variation within subject for the repeated measures. Missing data will be maintained as missing. The Least Square (LS) means of each treatment group, and the differences between each

SUVN-502 dose group (50 mg and 100 mg) and placebo will be reported for Weeks 4, 13 and 26, along with the corresponding 95% confidence intervals and p-values.

Sensitivity analyses to assess the impact of missing data will be conducted. These analyses will utilize the same methods as described previously. One analysis will use the EP analysis set and another will use the mITT population but will impute missing data using LOCF. If warranted, additional analyses may be investigated.

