4.2.2 Visit Windows

Assessments will be classified based on the visit information reflected on the eCRF. Assessments taken outside of protocol allowable windows will be assigned based on the closest scheduled visit. If there are assessments recorded on a day that is equidistant between two visits, the assessments will be attributed to the later visit. The only exception to this rule is for assessments recorded between Baseline and Week 4. Any assessment recorded after the Baseline visit will be mapped to Week 4 even if the day is closer to the Baseline visit. The timetable of visits is given in Section 7.1 in the protocol. Nominal study visits (Weeks relative to Baseline) will be used to summarize data presented by visit.

If subjects have more than one observation for a given time point, the average of the measurements will be used. This rule applies to efficacy data. For safety data, unless otherwise specified, if there is a repeated evaluation, the worst value will be used. If values are equal, the latest repeated (latest) value will be used.

If subjects withdraw early from the study, all study assessments at the early withdrawal visit will be assigned based on the rules described above. That is, they will be assigned to the closest scheduled visit. Data from subjects who discontinue but return after 4 weeks for the follow-up visit will be summarized with the Week 30 visits.

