4	Moderately severe	= subject has difficulty more than 50% of the time
5	Severe	= one or two word utterance; fluent, but empty speech; mute

The total score for the ADAScog-11 is the sum of the above 11 items. The maximum score is 70 points. A lower score indicates a better performance.

If any item is not administered because the subject is too cognitively impaired to complete, then the subjects receives the maximum amount of points for that item. Any other reason for not administering the item on the eCRF will be left as missing. Handling of missing items in the ADAScog-11 is summarized in [Section 4.7.1.2](#).

Summary

ADAScog-11 scores will be summarized by treatment group and visit in terms of absolute values and changes from baseline, both for the observed case and LOCF analyses.

A listing of observed and change from Baseline value will be provided.

Analysis

A MMRM will be used to test the hypotheses stated in [Section 4.7.1](#) that there is no difference between SUVN-502 and placebo in the mean change from baseline at Week 26 for the ADAScog-11 score. The LS means of each treatment group, and the differences between each SUVN-502 dose group and placebo will be reported for Weeks 4, 13, and 26, along with the corresponding 95% confidence intervals and p-values.

The change from baseline score at each scheduled post-baseline visit (according to the Study Schedule) during the treatment period will be the dependent variable. The model will include the fixed effects of treatment, week, treatment-by-week interaction, and APO-E status (carrier- one allele, carrier- two alleles, and non-carrier), as well as a continuous covariates of baseline score, the baseline score-by-week interaction, age, and Baseline MMSE score. Pooled site, as defined in [Section 4.2.4](#), will be included as a random effect. Week will be considered a categorical variable with values equal to the visit numbers at which the scales were assessed. An unstructured covariance matrix will

initially be used to model the within-subject variance-covariance errors. The following SAS code will be used to perform the analyses:

```
PROC MIXED;  
CLASS treat week subjid apoe site;  
MODEL outcome = treat week treat*week base base*week apoe mmse_base age /  
          DDFM=kr;  
RANDOM site;  
REPEATED week / SUBJECT=subjid TYPE=UN;  
LSMEANS treat/ cl diff;  
RUN;
```

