4.10 Determination of Sample Size

A total of 537 subjects will be randomized into one of three treatment groups, SUVN-502 (50 mg), SUVN-502 (100 mg) or placebo (179 subjects per group). With a sample size

of 537, there is at least 80% power to detect a 2-point drug-placebo difference on the ADAScog-11 with a standard deviation of 6, assuming a 2-sided 5% significance level and a drop-out rate of 20% or less.

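### The zLOCF sensitivity analysis counts imputed scores as observed, so its interval is too narrow, and the SAP's claim that it is unbiased is too general

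*SAP*

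**What the plan says.** SAP 4.7.1.2 leaves missing total scores missing in the primary MMRM. For the sensitivity analysis of the primary and secondary endpoints, "missing total scores will be imputed using the z-score Last Observation Carried Forward (zLOCF) approach prior to analysis". A missing score becomes the value lying as many standard deviations from the subject's treatment-group mean at that visit as the last observed score did at its own visit. Group means are then recalculated with the imputed values included, and one final value per missing score is analysed by the same method as observed data. SAP 4.7.1.1 attaches 95% intervals and p-values to that method. No variance correction is given.

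The SAP states two conditions under which zLOCF is unbiased: missing at random within treatment group, or "missing at random after taking into account the severity at the time of dropout".

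Three other places bear on this:
- SAP 4.10 plans for "a drop-out rate of 20% or less".
- SAP 4.2.2: for early withdrawals, "all study assessments at the early withdrawal visit will be assigned based on the rules described above", meaning the closest scheduled visit. Two efficacy scores at one visit are averaged.
- The protocol named plain LOCF. Its Synopsis says "Sensitivity analyses for the primary and secondary variables using last observation carried forward (LOCF) and using the EP analysis set will be conducted", and section 8.5.1.2 says "One analysis will use the EP analysis set and another will use the mITT population but will impute missing data using LOCF". SAP 4.7.2 still lists summaries "both for the observed case and LOCF analyses".

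**The concern.** An imputed score made from an estimated arm mean and an earlier score is not a new measurement. Counting it as one overstates the information at Week 26 and shrinks the standard error, and the shortfall grows with the share imputed.

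The second unbiasedness condition also looked too strong. zLOCF holds a dropout's z-score constant, with no regression to the mean. If sicker subjects leave, the arm means shift. The shifts cancel in the treatment difference only when the arms are alike in the relevant respects.

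Finally, zLOCF places each dropout around the later mean of that subject's own arm, so it hands an active-arm dropout the active-arm effect. At stake is misplaced reassurance: a supportive result that looks more precise, and more informative about dropouts, than it is.

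**Working it through.** **Inputs.** SAP 4.10: 179 per arm, 2-point difference, SD 6, two-sided 5%, dropout up to 20%. Protocol schedule: visits at Days 28, 91 and 182. SAP 4.7.1.2: two-pass zLOCF within arm. The documents give no between-visit variances, so these are assumed. Setting A has person/slope/error SDs of 6/1.5/4.0 and setting B has 9/3.5/3.4. Both give an SD of 26-week change of 5.8–5.9, close to the planned 6.

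**1. The plan's own figure.** 2 × (1.96 + 0.8416)² × 6² / 2² = 141.3, so 142 per arm, or 143 with the t distribution. 143 / 0.8 = 178.75, which gives 179 per arm and 537 in total. The sample size reproduces.

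**2. Benchmark for the interval.** SE = 6√(2/n). Suppose a fraction m of Week 26 scores is missing. Counting all 179 per arm rather than the 179(1 − m) observed makes the SE too small by 1 − √(1 − m).
- m = 20%: 6√(2/179) = 0.634 against 6√(2/143.2) = 0.709, a shortfall of 10.6% (half-width 1.24 against 1.39).
- m = 15%: 7.8%. m = 10%: 5.1%. m = 7.5%: 3.8%.

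**3. Effect of visit mapping.** The visit midpoints are (28 + 91)/2 = 59.5 and (91 + 182)/2 = 136.5. If dropout days are spread evenly over Days 0–182 (assumed), (182 − 136.5)/182 = 25% of dropouts have a withdrawal score classed as Week 26. So 10% dropout leaves 7.5% missing, and 20% leaves 15%.

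**4. Simulation under random dropout, no true effect.** 20,000 trials per case, 179 per arm, two-pass zLOCF, then a baseline-adjusted Week 26 comparison. That comparison stands in for the MMRM on completed data; age, MMSE, APO-E and site are omitted. The ratio is model SE to true SE.

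| Dropout | Mapped | Ratio A / B | SE too small by | Null rejection |
|---|---|---|---|---|
| 10% | yes | 0.962 / 0.966 | 3–4% | 5.8–5.9% |
| 20% | yes | 0.910 / 0.922 | 8–9% | 7.3–7.5% |
| 10% | no | 0.932 / 0.948 | 5–7% | 6.5–6.7% |
| 20% | no | 0.884 / 0.889 | 11–12% | 8.1–8.6% |

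Simulation error is about 0.005 in the ratio and 0.002 in the rejection rate. A different set of assumed variances and correlations, unmapped, gave ratios of 0.84–0.91 at 20%. For comparison, multiple imputation gave ratios of 0.98–1.03 and rejection of 4.5–5.5%.

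**5. The unbiasedness statement.** Dropout driven by the score itself, unmapped, settings A / B, from two separate simulations:
- 10% against 20% dropout: bias in the difference 0.21 / 0.08 and 0.21 / 0.06.
- 20% dropout depending on severity in one arm only: 0.42 / 0.21 and 0.40 / 0.20.
- Same mechanism and 20% rate in both arms, but a wider spread of active-arm scores at Week 26 (effect varying between subjects with SD 4, assumed): 0.21 / 0.19 and about 0.23 / 0.15.
- Same mechanism and rate with a uniform 2-point effect: within 0.02.

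Score-driven cases were not run with mapping. With dropout driven by change from baseline, mapping reduced the 10%-against-20% bias from 0.15–0.24 to 0.08–0.11.

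**6. Lost benefit, as a what-if.** If active-arm dropouts lost a 2-point effect entirely, the all-randomized difference would be 2 × 0.90 = 1.80 at 10% missing and 2 × 0.80 = 1.60 at 20%. zLOCF returned 1.94–2.03. The MMRM returned 1.99 and 2.00.

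**7. Tipping points at planning values.** Adding δ to imputed active-arm scores moves the difference by m × δ, so the result tips at δ = (2 − 1.96 × SE)/m. This holds the SE at its observed-data value.
- m = 20%: (2 − 1.96 × 0.709)/0.20 = 3.1.
- m = 15%: (2 − 1.96 × 0.688)/0.15 = 4.3.
- m = 10%: (2 − 1.96 × 0.669)/0.10 = 6.9.

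**The case against.** **It is only a supportive analysis in a phase 2A trial.** True. A reader might infer that the primary test is compromised. It is not: the primary MMRM imputes no missing total score by zLOCF.

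**The larger shortfalls ignore the SAP's own mapping rule.** This stands, so the mapped figures are the headline. The unmapped ones show what happens if few withdrawal scores fall near Week 26.

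**No document makes loss of benefit after dropout a target.** This stands. A reader might infer that the SAP is wrong to lack a delta-adjusted or reference-based analysis, but the documents do not support that. Parts of SAP 4.4, 4.7.1.5 and 4.7.2 are also redacted, so absence cannot be fully established. What remains is a limit on interpretation. The data will not fill the gap either. Of the early-termination visit, Protocol 7.2.7 says "This visit should take place as soon as possible after the subject stops taking study drug", and Week 30 has no ADAS-Cog.

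**The SAP allows further sensitivity analyses.** It does, but only if missingness differs from what was expected, and it specifies none.

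**The SAP departs from the protocol's LOCF.** A reader might infer a breach. Protocol 8 leaves detailed methods to the SAP, and Protocol 8.2 leaves imputation details to it, so the change only needs to be noted.

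**Could the unbiasedness sentence be repaired rather than cut?** It is tempting to say that the treatment difference is unbiased whenever both arms share dropout mechanism and rate. That is also too general, as the unequal-spread case in the check shows.

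**Conclusion.** The point holds as a fault in the sensitivity analysis. Its interval and p-value are too narrow as written: the SE is about 3–4% too small at 10% dropout and 8–9% at the 20% ceiling under the SAP's mapping. The direction does not depend on the assumed variances or dropout timing, but the exact percentages do.

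The second unbiasedness condition is not true in general. The treatment difference is biased when dropout rate, mechanism or later spread of scores differs by arm. Without mapping, illustrative bias is about 0.1–0.2 points at 10% against 20% dropout and about 0.2–0.4 points when only one arm's 20% dropout depends on severity. Mapping should make these smaller. They also rest on the assumed strength of the dropout mechanism.

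Agreement between zLOCF and the MMRM should not be reported as evidence about subjects who lose benefit after stopping drug.

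**What to change.** Keep the primary MMRM. Before database lock, which SAP 4.11 permits, revise SAP 4.7.1.2:

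1. Make multiple imputation under Rubin's rules the inferential sensitivity analysis. Within arm, impute Week 13 and then Week 26 ADAScog-11 from baseline, earlier scores and the MMRM covariates. State the number of imputations and the seed. Keep zLOCF, if at all, as descriptive only.
2. Delete the second unbiasedness condition ("missing at random after taking into account the severity at the time of dropout" and its joining word) and put nothing in its place.
3. As a low-cost addition on the same imputations, prespecify a tipping-point analysis at Week 26 that adds δ to imputed active-arm scores. A range of 0 to 8 points, for example, would cover the tipping points of 3.1, 4.3 and 6.9 calculated at planning values.
4. State whether LOCF in the SAP 4.7.2 summaries means LOCF or zLOCF, and note the move from the protocol's plain LOCF.

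The cost is one revised section and modest programming, with no new data and no change to sample size or primary analysis. The downside is that the δ range must be justified and the sensitivity result may look less favourable.
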